4.2.3. Primary Analysis Time Point, Months 3 and 12, and Treatment Period

The primary analysis time point is defined as the average of Weeks 23, 25, and 27. If 1 or 2 of the 3 assessments are missing, then non-missing assessments will be used. Month 3 is defined as the average of Weeks 13 and 17. Month 12 is defined as the average of Weeks 51 and 53. For Month 3 or Month 12, if 1 assessment is missing, then non-missing assessment will be used.

The treatment period is defined as the time period from the first dose administration to the earliest date from 42 days after the last dose of Study Drug and last contact date within the study.

4.2.4. Visit Windows

The efficacy and exploratory measures will be mapped to analysis visits according to the visit windows in the table below.

The intent of these visit windows is not to align with those prescribed for visit scheduling in the study protocol but, rather, based on the protocol-defined target study day, to delineate mutually exclusive windows so that all efficacy assessments proximal to a particular study week can be integrated to best represent the patient's status during that period of the study. Visits after Week 53 are part of the post-treatment assessment period and, due to the fact that most patients are expected to roll into the OLE study, these data will only be provided in patient listings for evaluation of individual patient safety rather than being tabulated. Therefore, no visit windows are needed for data analysis for these visits. If a patient discontinued early from the treatment period but attended applicable landmark visits to collect efficacy assessments, then those assessments should be mapped to analysis visits and utilized in the analyses as well, unless otherwise stated.

For Daily FCS Symptoms questionnaire using average, data in the same visit window will be averaged.

For Daily FCS Symptoms questionnaire using the highest (worst) score, the highest score in each visit window will be determined.

For other data, if there are multiple assessments within a visit window, the assessment nearest the target day will be used unless two assessments are equally near, in which case the average value will be used. For lipid data, local lab data will not be used unless central lab assessments are not available at certain visit. When calculating the baseline and analysis endpoints, only if the data from central lab is missing, then the local lab data will be utilized.

ISIS 678354-CS3

Statistical Analysis Plan

Efficacy/PD measure	Nominal Visit (Target Day)	Analysis Visit Window (Day)
Lipid Panel	Week 5 (Day 29)	2-43
	Week 9 (Day 57)	44-71
	Week 13 (Day 85)	72-99
	Week 17 (Day 113)	100-127
	Week 21 (Day141)	128-148
	Week 23 (Day 156)	149-162
	Week 25 (Day 169)	163-176
	Week 27 (Day 183)	177-190
	Week 29 (Day 197)	191-225
	Week 37 (Day 253)	226-281
	Week 45 (Day 309)	282-330
	Week 51 (Day 351)	331-358
	Week 53 (Day 365)	359-379ª
Daily FCS Symptoms	Week 2 (Day 8)	2-8
	Week 3 (Day 15) – Week 53 (Day 365)	(Week-1)*7-5 to (Week-1)*7+1
FCS Impacts; Pain Interference &	Week 5 (Day 29)	2-43
PGIS	Week 9 (Day 57)	44-71
	Week 13 (Day 85)	72-99
	Week 17 (Day 113)	100-127
	Week 21 (Day141)	128-148
	Week 23 (Day 156)	149-162
	Week 25 (Day 169)	163-176
	Week 27 (Day 183)	177-190
	Week 29 (Day 197)	191-211
	Week 33 (Day 225)	212-239
	Week 37 (Day 253)	240-267
	Week 41 (Day 281)	268-295
	Week 45 (Day 309)	296-323
	Week 49 (Day 337)	324-344
	Week 51 (Day 351)	345-358
	Week 53 (Day 365)	359-379 ^a
PGIC	Week 23 (Day 156)	149-162
	Week 25 (Day 169)	163-176
	Week 27 (Day 183)	177-190
	Week 51 (Day 351)	331-358
	Week 53 (Day 365)	359-379 ^a
Health-related QOL (PROMIS 29+2	Week 13 (Day 85)	72-99
Profile v2.1) & PROMIS Cognitive	Week 23 (Day 156)	149-162
Function	Week 25 (Day 169)	163-176
	Week 27 (Day 183)	177-190
	Week 51 (Day 351)	331-358
	Week 53 (Day 365)	359-379 ^a

^a 379 represents the middle point between the target days for the Week 53 visit and the first post-treatment assessment visit.

ISIS 678354-CS3

All other by-visit assessments will be summarized using the visit labels provided in the data. Multiple results with the same visit label will be averaged. Unscheduled results from the central lab will not be included in the by-visit summaries but will be used in the determination of baseline, laboratory abnormality summaries and shift analyses, and presented in data listings. Local lab data will be only used in platelet analyses (including by visit summary, abnormality summaries, and shift from Baseline to worst post-baseline), and presented in data listings. For other safety lab parameters, local lab data will not be included in any analyses and data summaries.

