8.5. Safety Monitoring Rules

Stopping rules are described below in Section 8.6.

Please refer also to the 'Guidance for Investigator' section of the Investigator's Brochure.

- For the purposes of safety monitoring Baseline is defined as the average of the Day 1 pre-dose assessment and the last measurement prior to Day 1.
- In addition to the standard monitoring of clinical safety parameters, the following guidelines are provided for the monitoring of selected parameters chosen based on preclinical and clinical observations.
- In case of discrepancy between the test results from 2 sources, such as between the central and local lab, safety-mandated action must be initiated based on the more critical (lower or higher, as relevant) of the 2 values.

Confirmation Guidance: At any time during the study (Treatment or Post-Treatment Periods), the clinical laboratory results meeting any of the safety monitoring criteria presented below **must be confirmed** by performing measurements (ideally in the same laboratory that performed the

initial measurement) on new specimens. All new specimen collections should take place as soon as possible (ideally within 3 days but no later than 7 days of the initial collection). For stopping rules, if the initial laboratory result is observed during the Treatment Period, the results from the retest **must be available** prior to administering the next dose of Study Drug.

Re-dosing Guidance: In the event the initial laboratory result meets a stopping criterion, the results from the retest **must be available and reviewed by a Medical Monitor** prior to administration of the next dose of Study Drug (ISIS 678354 or placebo). In general, patients who do not meet the stopping rules based upon retest may continue dosing. However, the Investigator and the Sponsor Medical Monitor (or appropriately qualified designee) should confer as to at which dose Study Drug should be restarted, and whether additional close monitoring of the patient is appropriate. If any of the stopping criteria described below (refer to Section 8.6.1 through Section 8.6.3) are met, the patient will be permanently discontinued from further treatment with Study Drug (ISIS 678354 or placebo), evaluated fully as outlined below and in consultation with the Sponsor Medical Monitor or appropriately qualified designee, and will be followed up in accordance with Section 8.8 of the protocol.

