8.5.1. Safety Monitoring Rules for Liver Chemistry Tests

The following rules are adapted from the draft guidance for industry, "Drug-Induced Liver Injury: Premarketing Clinical Evaluation," issued by the U.S. Department of Health and Human Services, Food and Drug Administration, July 2009. For a definition of Baseline, please refer to guidance in Section 8.5 above.

All patients will have liver chemistry tests monitored every 14 days (± 2 days) for the first 3 months of the Treatment Period, and monthly thereafter during the Treatment Period. Upon completion of the study Treatment Period, liver chemistry tests should be monitored as per visit schedule in Appendix A.

In the event of appearance of symptoms or signs of hepatic injury (jaundice, fatigue, nausea, vomiting, right upper quadrant pain or tenderness, fever, rash, abnormal bleeding or bruising, or eosinophilia > ULN) liver enzymes and bilirubin should be tested as soon as possible (ideally within 3 days). Testing at a lab that is local to the patient is permissible for this purpose.

In the event of an ALT or AST measurement that is $> 3 \times ULN$ (or the greater of 2 × baseline value or 3 × ULN if the baseline value was > ULN) at any time during the study (Treatment or Post-Treatment Period), the initial measurement(s) should be confirmed as described in Section 8.5.

Frequency of Repeat Measurements: Patients with confirmed ALT or AST levels $> 3 \times$ ULN (or the greater of 2 × baseline value or 3 × ULN if the baseline value was > ULN) should have their liver chemistry tests (ALT, AST, alkaline phosphatase [ALP], INR and total bilirubin) retested at least once weekly until ALT and AST levels become $\le 1.2 \times$ ULN or $1.2 \times$ baseline if the baseline value was > ULN.

Further Investigation into Liver Chemistry Elevations: For patients with confirmed ALT or AST levels $> 3 \times ULN$ (or the greater of 2 × baseline value or 3 × ULN if the baseline value was > ULN), the following evaluations should be performed:

- Obtain a more detailed history of symptoms and prior and concurrent diseases
- Obtain further history for concomitant drug use (including non-prescription medications, herbal and dietary supplement preparations), alcohol use, recreational drug use, and special diets
- Obtain a history for exposure to environmental chemical agents and travel
- Serology for viral hepatitis (HAV IgM, HBsAg, HCV antibody, cytomegalovirus (CMV) IgM, and EBV antibody panel)

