The number and percent of patients falling in each of the following categories based on results after first dose will be tabulated by treatment group. The risk different (95% CI) in the crude incidence rates between each active treatment group (or total ISIS 678354) and pooled placebo group will be provided for selected categories.

- ALT or AST \geq ULN
- The higher of ALT/AST \ge 3 × upper limit of normal (ULN) or ALT/AST \ge 2 × Baseline (i.e., ALT/AST \ge 3 × ULN and ALT/AST \ge 2 × Baseline)
- ALT/AST \geq 3 × ULN
- ALT/AST \geq 5 × ULN
- ALT/AST $\geq 8 \times ULN$
- $ALT/AST \ge 10 \times ULN$
- ALT/AST $\geq 20 \times ULN$
- Highest ALT falling in: ≥ 3 × ULN < 5 × ULN, ≥ 5 × ULN < 10 × ULN, ≥ 10 × ULN -< 20 × ULN (the risk difference will not be provided for this category)
- Total bilirubin $\geq 2 \times ULN$
- Total bilirubin $\geq 5 \times ULN$
- Total bilirubin $\ge 8 \times ULN$
- ALT or AST \geq 3 × ULN and Total bilirubin \geq 2 × ULN
- $ALP \ge 2 \times ULN$ and (baseline $ALP < 2 \times ULN$ or baseline ALP missing)
- Direct bilirubin $\ge 2 \times ULN$
- Direct bilirubin $\geq 5 \times ULN$

- GGT $\ge 2 \times ULN$
- ALT \geq 3 × ULN and INR \geq 1.5
- $ALP \ge 2 \times ULN$
- ALP \geq 3× ULN
- INR $\geq 1.5 \times ULN$
- INR \geq 3 × ULN
- INR \geq 5 × ULN

The number and percent of patients falling in each of the following categories based on confirmed results after first dose will be tabulated by treatment group (a confirmed value is based on a consecutive lab value performed on a different day to, but within 10 days of, the initial value. If that value is in the same or worse category then the initial value is confirmed. If the consecutive value is in a better category then the initial value is confirmed using the consecutive value category. If there is no retest within 10 days then the initial value is presumed confirmed. If there are multiple results on the same day, then the worst value will be utilized in the analysis):

- The higher of ALT/AST \ge 3 × ULN or ALT/AST \ge 2 × Baseline, which is confirmed
- ALT/AST \geq 3 × ULN, which is confirmed
- ALT/AST \geq 5 × ULN, which is confirmed
- ALT/AST $\geq 10 \times$ ULN, which is confirmed
- ALT/AST $\geq 20 \times$ ULN, which is confirmed

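### Local-laboratory liver and kidney results are barred from every safety table, so an abnormality seen only locally would be listed, and probably reported as an AE, but not counted in the laboratory threshold, eDISH or shift outputs

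*Combined protocol and SAP*

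**What the plan says.** SAP 4.2.4 sets three rules for safety laboratory data.

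- "Local lab data will be only used in platelet analyses", where it enters by-visit, abnormality and shift summaries. Local data also go to listings.
- "For other safety lab parameters, local lab data will not be included in any analyses and data summaries".
- Unscheduled central results are left out of by-visit summaries but "will be used in the determination of baseline, laboratory abnormality summaries and shift analyses, and presented in data listings".

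SAP 4.10.5 then defines the outputs concerned: ALT/AST, bilirubin, ALP, GGT and INR categories, combined liver categories, confirmed ALT/AST categories, eDISH plots, creatinine, eGFR, UACR and UPCR categories, and shifts to the worst post-baseline value. For confirmed values it adds: "If there is no retest within 10 days then the initial value is presumed confirmed".

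On the protocol side, routine liver and renal samples go to the central laboratory every 14 days for three months and monthly after that (6.2.1). If symptoms or signs of hepatic injury appear, 8.5.1 asks for prompt testing and says: "Testing at a lab that is local to the patient is permissible for this purpose". Section 8.5.2 says the same for renal dysfunction. Where two sources disagree, 8.5 requires that "safety-mandated action must be initiated based on the more critical (lower or higher, as relevant) of the 2 values". Section 6.2.1 has sites enter local results in the eCRF.

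**The concern.** The protocol uses local results to decide what happens to a patient, but the SAP does not use them to describe what happened. Local liver and renal results are unlikely to be a random sample, because many would be drawn when a patient had symptoms or a value needed checking. Leaving them out could remove the values of most interest from the threshold tables.

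The SAP gives no reason for the difference in treatment. Platelets take local values throughout, and lipids fall back on them when the central value is missing (4.2.4). Liver and renal tests have their own stopping rules (protocol 8.6.1, 8.6.2) and get neither. With about 20 patients per arm, the rare liver categories, such as ALT or AST at 3 × ULN or more together with bilirubin at 2 × ULN or more, will probably hold zero or one patient, so one uncounted patient matters to the reading.

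**Working it through.** The plan states no figure on this point, so there is none to reproduce. The check follows a result through the documents and then sizes one omitted patient.

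**1. A symptom-prompted local ALT, AST or creatinine.** Testing may be local (8.5.1, 8.5.2). The result is entered in the eCRF (6.2.1) and can drive action if it is the more critical value (8.5). A retest is ideally done by the laboratory that gave the first result (8.5), so the confirmation may be local too. Under SAP 4.2.4 neither value enters the 4.10.5 threshold categories, eDISH plots or shift tables. No other SAP section reverses this.

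**2. A central ALT or AST elevation retested only locally.** The local retest cannot be used, so for the SAP there is no retest within 10 days and the central value is presumed confirmed, even if the local result was normal. This affects only ALT and AST. The other confirmed-value tables are for platelets, where local data are used.

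**3. When a patient is actually lost.** Scheduled and unscheduled central results both count in the abnormality and shift tables. A patient drops out of a category only if no central sample meets the same criterion. The longest routine gap is the monthly interval after Month 3.

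**4. Size of one omitted patient.** The change in an arm's rate is 1/n.

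| Group | n | Source | 1/n |
|---|---|---|---|
| Each active arm, planned | 20 | 30 per cohort, randomized 2:1 | 5.0 points |
| 50 mg, treated | 21 | plain-language summary | 4.8 points |
| 80 mg, treated | 22 | plain-language summary | 4.5 points |
| Pooled active, treated | 43 | 21 + 22 | 2.3 points |

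**5. Effect on a risk difference.** SAP 4.10 uses Miettinen-Nurminen intervals. The limits are the values of δ that solve (d − δ) / √{[p₁(1 − p₁)/n₁ + p₂(1 − p₂)/n₂] × N/(N − 1)} = ±1.96. Here d is the observed difference, p₁ and p₂ are the maximum-likelihood estimates restricted to p₁ − p₂ = δ, and N = n₁ + n₂. Take 80 mg (n₁ = 22) against pooled placebo (n₂ = 23), with no placebo events. The number of local-only patients in the 80 mg arm is an assumption, varied from 0 to 3.

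| Local-only patients | Difference (points) | 95% CI |
|---|---|---|
| 0 | 0.0 | −14.6 to 15.2 |
| 1 | 4.5 | −10.4 to 22.1 |
| 2 | 9.1 | −6.2 to 28.1 |
| 3 | 13.6 | −2.0 to 33.6 |

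Hand check of the first row: the upper limit is c/(1 + c), with c = 3.8415 × 45/(44 × 22) = 0.1786, which gives 15.2 points. With 23 in place of 22, c = 0.1708 and the lower limit is −14.6. If these were the only qualifying patients, the SAP rule would print the first row in every case.

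**The case against.** A single central method is a defensible choice, and several points on that side stand.

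- **Local testing is allowed, not directed.** A reader might infer that the protocol sends suspected organ injury to local laboratories. It does not: routine samples are central, and discretionary local tests are described as additional to the required central ones.
- **The results are not hidden.** A reader might infer that a patient stopped on a local value would show no abnormality anywhere in the tables. That goes too far. Local data are in the listings. Protocol 9.3.1 counts as an AE a laboratory deterioration that comes with symptoms or changes treatment, so such a patient should reach the TEAE, discontinuation, dose-interruption, liver and renal event summaries (SAP 4.10.1, 4.10.2, 4.10.4.7, 4.10.4.8). This cover is good but incomplete. Protocol 9.5.1 prefers a diagnosis to a laboratory term and keeps results judged not clinically significant out of AE reporting, and AE tables do not give the threshold rates that 4.10.5 sets out.
- **The presumed-confirmed rule is conservative.** It follows the protocol's own convention for unconfirmed liver values (8.6.1), and a central result retested only locally departs from the stated preference for the same laboratory. The effect is a possible over-count.
- **The platelet rule has its own rationale.** Section 6.2.1 gives clotting, clumping and hemolysis as reasons for local hematology testing. That reason does not carry over to chemistry.
- **Mixing assays adds noise.** Protocol 2.1 notes that lactescent plasma interferes with other assays. Creatinine and eGFR categories are changes from baseline, and UACR and UPCR are mostly absolute cut-offs, so ULN scaling does not help. A local creatinine set against a central baseline could create a spurious 0.3 mg/dL rise.

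The last point limits the renal part of the remedy. None of these points explains why locally observed liver values should be absent from every threshold table.

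**Conclusion.** The exclusion is explicit, and it sits badly with a protocol that permits local testing for suspected injury and acts on the result. An abnormality seen only locally would be listed and probably reported as an AE. It would not count in the threshold categories, the ALT/AST confirmed-value tables, the eDISH plots or the worst-value shifts. For confirmed ALT/AST the error can go either way: a peak seen only locally is missed, and a central elevation that only a local retest contradicts is kept.

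The size rests on an unknown, the number of patients whose only qualifying value is local. Each would change an active arm's rate by about 4.5 to 5 points. In a rare liver category that can be the difference between none and one. A reader might infer that the planned counts and risk differences will be wrong. The documents do not support that: the tables are affected only if such patients exist and no central sample meets the same criterion, and even three against none leaves an interval that includes zero. This is a gap worth closing at low cost. It does not show that the safety analysis is unsound.

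**What to change.** Amend SAP 4.2.4 and 4.10.5 as follows.

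1. Keep by-visit summaries central-only.
2. Include local ALT, AST, ALP and bilirubin, as multiples of the local ULN, and local INR in the any-time post-baseline categories. Carry the relevant values into the ALT/AST confirmed-value tables, the worst-value shift tables and the eDISH plots. Flag every local value. At minimum, produce a parallel sensitivity version of these outputs with local values included.
3. Show local creatinine/eGFR and UACR/UPCR in a separate flagged supplementary table, and do not merge them with the central categories.

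No extra samples are needed. The cost is some programming and capture of local reference ranges; protocol 6.2.1 mentions entry of results but not of ranges. Between-laboratory and assay variation, including lipemic interference, will enter some outputs. The flag, and showing results with and without local values, lets a reader judge how much that matters.

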4.3. Software

All report outputs will be produced using SAS[®] Version 9.4 or a later version in a secure and validated environment.

4.4. Study Subjects

4.4.1. Disposition of Subjects

A clear accounting of the disposition of all subjects who enter the study will be provided, from screening to study completion.

The following summaries will be provided:

- A summary of the number and percentage of subjects who were screened, randomized, and subjects who are excluded prior to randomization by major reason and overall, using the all screening patients.
- A summary of the number and percentage of patients treated (with at least one dose or partial dose of IMP) and terminating from treatment, and the number and percentage of major reason of patient terminating from treatment by treatment group, total ISIS 678354-treated (50 mg +80 mg) and overall.
- A summary of the number and percentage of patients completed the study and terminating from the study, and the number and percentage of major reason of patient terminating from the study, by treatment group, total ISIS 678354-treated (50 mg + 80 mg) and overall.
- The percentage of patients treated, the percentage of patients who discontinued from treatment and the percentage of patients who discontinued from study will be calculated based on the number of patients randomized.

A by-subject listing of disposition data will be provided based on the randomized subjects. Listing of eligibility criteria will be provided. A separate disposition listing for screen failures will also be provided.

4.4.2. **Protocol Deviations**

Protocol Deviations (PDs) will be classified as "major" or "minor" based on study protocol deviation guidance. All protocol deviations and major protocol deviations will be summarized by deviation category. The PD summaries will include the number and percentage of subjects with a PD by treatment group and overall, and by type of deviation, based on the randomized subjects. All protocol deviations will be listed.

Significant protocol deviations are defined as those deviations from the protocol likely to impact the perceived efficacy and/or safety of study treatments. The impact of significant protocol deviations on

ISIS 678354-CS3

the efficacy and/or safety results will be investigated by assessing the robustness of the study results and conclusions to the choice of analysis set, both including and excluding data potentially affected by significant protocol deviations. Before unblinding, the data will be reviewed by the clinical group for identification of significant protocol deviations.

